10.5.2 Columbia-Suicide Severity Rating Scale

For C-SSRS, the number and percentage of subjects with suicidal ideation or suicidal behavior as recorded on the C-SSRS will be summarized for the Safety Populations 1 and 2. The distribution of responses for most severe suicidal ideation and most severe suicidal behavior in the subject's lifetime history, in the past 6 months, in the open-label treatment period (atogepant treatment period, atogepant + ubrogepant treatment period, and overall), and in the follow-up period will also be presented. Supportive listings will be provided and will include the PID number, study center number, lifetime history, and postbaseline

values. Intensity of suicidal ideation and suicidal behavior type will also be included in these listings.

10.6 Safety Subgroup Analyses

Two subgroups will be applied in subgroup analyses based on subjects' ubrogepant use:

Subgroup by number of ubrogepant use days:

- Never used ubrogepant
- Low ubrogepant use: 1-3 days of ubrogepant taken in the atogepant + ubrogepant treatment period
- Moderate ubrogepant use: 4-9 days of ubrogepant taken in the atogepant + ubrogepant treatment period
- High ubrogepant use: ≥ 10 days of ubrogepant taken in the atogepant + ubrogepant treatment period

Subgroup by number of ubrogepant doses taken:

- Never used ubrogepant
- Low ubrogepant use: 1-6 doses of ubrogepant taken in the atogepant + ubrogepant treatment period
- Moderate ubrogepant use: 7-18 doses of ubrogepant taken in the atogepant + ubrogepant treatment period
- High ubrogepant use: 19+ doses of ubrogepant taken in the atogepant + ubrogepant treatment period

TEAE, serious TEAE, and TEAE leading to study drug discontinuation will be summarized by subgroups.

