5.5 Withdrawal of Subjects and Discontinuation of Study

A subject may voluntarily withdraw or be withdrawn from the study at any time for reasons including, but not limited to, the following:

- Clinically significant abnormal laboratory results or AEs, which rule out continuation of the study drug, as determined by the investigator or the sponsor.
- The investigator believes it is in the best interest of the subject.
- The subject requests withdrawal from the study.
- Eligibility criteria violation was noted after the subject started study drug and continuation of the study drug would place the subject at risk.
- Introduction of prohibited medications or dosages and continuation of the study drug would place the subject at risk.
- The subject becomes pregnant during the study.
- The investigator determines the subject is significantly noncompliant with study procedures.
- Subject meets one of the following criteria for ALT/AST elevations, and is advised not to be rechallenged:
 - ALT or AST $\geq 3 \times$ ULN and the subject is symptomatic with the appearance of fatigue, nausea, vomiting, right upper quadrant pain or tenderness, fever, rash, or eosinophilia ($> 5\%$)
 - ALT or AST $\geq 3 \times$ ULN and total bilirubin $> 2 \times$ ULN
 - ALT or AST $\geq 3 \times$ ULN and international normalized ratio (INR) > 1.5
 - ALT or AST $\geq 5 \times$ ULN for more than 2 weeks
 - ALT or AST $\geq 8 \times$ ULN
- Subjects who reply with "yes" to Questions 4 or 5 in the suicidal ideation section or "yes" to any question in the suicidal behavior section for the C-SSRS at Visits 2 through 9 must be withdrawn from the study and should receive appropriate follow-up as in routine clinical practice, including Early Termination Visit and Safety Follow-up (Visit 9).

For subjects to be considered lost to follow-up, reasonable attempts must be made to obtain information on the subject's final status. At a minimum, 2 telephone calls must be made and 1 certified letter must be sent and documented in the subject's source documentation.

AbbVie may terminate this study prematurely, either in its entirety or at any site. The investigator may also stop the study at his/her site if he/she has safety concerns. If AbbVie terminates the study for safety reasons, AbbVie will promptly notify the investigator.

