5.7 Study Drugs

Atogepant tablets, manufactured by AbbVie, will be taken orally with or without food once daily beginning on Day 1 in the clinic and should be taken at approximately the same time each day. If subjects should forget to take their atogepant dose at their regularly scheduled dosing time, they should take the forgotten dose as soon as they remember, and then take their next dose at the regularly scheduled dosing time.

Ubrogepant tablets, manufactured by AbbVie, will be taken orally with or without food as needed to treat up to 8 breakthrough migraine headaches for the 4 weeks between each visit for Visits 5 to 8. During this time, subjects will take a dose of ubrogepant 100 mg to treat their breakthrough migraine headache. If after 2 hours the migraine attack has not resolved or the migraine headache returns within 24 hours, subjects can choose either to take a second dose of ubrogepant 100 mg or any of the acute medications listed in Section 5.4.

All subject dosing will be recorded. The study site personnel will document compliance.

AbbVie will provide atogepant tablets and ubrogepant tablets. AbbVie-provided study drugs should not be substituted or alternately sourced, unless otherwise directed by AbbVie.

Atogepant tablets will be packaged in bottles with quantities sufficient to accommodate study design. Ubrogepant tablets will be packaged in blisters or packets with quantities sufficient to accommodate study design. Each kit will be labeled per local requirements and this label must remain affixed to the kit. Upon receipt, study drug should be stored as specified on the label and kept in a secure location at

the site. Each kit will contain a unique kit number. This kit number is assigned to a subject via the interactive response technology (IRT) and encodes the appropriate study drug to be dispensed at the subject's corresponding study visit. Site staff will complete all blank spaces on the label before dispensing to subjects. Study drug will only be used for the conduct of this study.

Upon completion of or discontinuation from study treatment, all original study drug units (containing unused study drugs) will be returned to the sponsor (or designee) or destroyed on site. All return or destruction procedures will be according to instructions from the sponsor and according to local regulations following completion of drug accountability procedures.

Study drugs are described in [Table 1](#).

Table 1. Study Drugs

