APPENDIX D. ACTIVITY SCHEDULE

The following table shows the required activities. The individual activities are described in detail in the Operations Manual ([Appendix F](#)).

Study Activities Table

Activity	Visit 1 Screening	Visit 2 Baseline	Visit 3	Visit 4	Visit 5	Visit 6	Visit 7	Visit 8 OR Early Termination	Visit 9 Safety Follow-Up Visit
	Week -1	Day 1 +3days	Week 4 ±3days	Week 8 ±3days	Week 12 ±3days	Week 16 ±3days	Week 20 ±3days	Week 24 +3days	Week 28 ±3days
❑ INTERVIEWS & QUESTIONNAIRES									
Informed consent	✓								
Eligibility criteria	✓	✓							
Medical/surgical history	✓								
Migraine history	✓								
Adverse event assessment	✓	✓	✓	✓	✓	✓	✓	✓	✓
Prior/concomitant therapy	✓	✓	✓	✓	✓	✓	✓	✓	✓
Patient-reported outcomes: HIT-6		✓	✓	✓	✓	✓	✓	✓	
Patient-reported outcomes: MSQ v2.1	✓	✓	✓	✓	✓	✓	✓	✓	
Patient-reported outcomes: WPAI:MIGRAINE		✓	✓	✓	✓	✓	✓	✓	
Patient-reported outcomes: PGIC (atogepant)					✓				
Patient-reported outcomes: PGIC (atogepant + ubrogepant)								✓	
Patient-reported outcomes: PHQ-4		✓	✓	✓	✓	✓	✓	✓	
Patient-reported outcomes: MTOQ-6						✓	✓	✓	
Patient-reported outcomes: Subject satisfaction with atogepant					✓			✓	
Patient-reported outcomes: subject satisfaction with ubrogepant								✓	

	Visit 1 Screening	Visit 2 Baseline	Visit 3	Visit 4	Visit 5	Visit 6	Visit 7	Visit 8 OR Early Termination	Visit 9 Safety Follow-Up Visit
Activity	Week -1	Day 1 +3days	Week 4 ±3days	Week 8 ±3days	Week 12 ±3days	Week 16 ±3days	Week 20 ±3days	Week 24 +3days	Week 28 +3days
Patient-reported outcomes: subject satisfaction with atogepant & ubrogepant								✓	
Investigator interviewer questionnaire migraine - screening	✓								
Investigator interviewer questionnaire migraine - Visit 2-5		✓	✓	✓	✓				
Investigator interviewer questionnaire migraine - Visit 6-8						✓	✓	✓	
C-SSRS	✓	✓	✓	✓	✓	✓	✓	✓	✓
LABORATORY & SITE EXAMINATIONS									
12-lead ECG	✓				✓			✓	
Height (screening only) and weight	✓	✓	✓	✓	✓	✓	✓	✓	✓
Vital signs	✓	✓	✓	✓	✓	✓	✓	✓	✓
Physical examination	✓							✓	✓
Urine pregnancy test	✓	✓	✓	✓	✓	✓	✓	✓	✓
CENTRAL LABORATORY									
Clinical laboratory tests	✓	✓	✓	✓	✓	✓	✓	✓	✓
PK (optional): predose at Visit 2		✓		✓				✓	
Biomarker samples (optional): predose at Visit 2		✓		✓				✓	✓
Pharmacogenetic sample – blood (optional)	✓								
Rx TREATMENT									
IRT entry	✓	✓	✓	✓	✓	✓	✓	✓	
Dispense study drug (atogepant)		✓	✓	✓	✓	✓	✓		
Dispense study drug (ubrogepant)					✓	✓	✓		
Perform drug reconciliation			✓	✓	✓	✓	✓	✓	

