5.0 Subject Disposition

Summaries will be provided for subjects in each of the following categories:

- Subjects who were screened;
- Subjects enrolled in the study;
- Subjects who completed the study (or did not with associated reasons);
- Subjects who discontinued the study drug, including atogepant and ubrogepant;
- Subjects who took at least one dose of study drug during the open-label atogepant treatment period (Safety Population 1);
- Subjects who completed open-label atogepant treatment period;
- Subjects who took at least one dose of study drug, either atogepant or ubrogepant, during the open-label atogepant + ubrogepant treatment period (Safety Population 2);
- Subjects who completed open-label atogepant + ubrogepant treatment period;
- Subjects who prematurely discontinued the open-label atogepant treatment period (including reasons for premature discontinuation);
- Subjects who prematurely discontinued the open-label atogepant + ubrogepant treatment period (including reasons for premature discontinuation);
- Subjects who prematurely discontinued the study (including reasons for premature discontinuation);
- Subjects in the mITT 1 Population;
- Subjects in the mITT 2 Population.

Screen failure subjects (i.e., subjects who consented to participate in the study but were not enrolled) and the associated reasons for failure to enroll will be summarized and listed for all screened subjects.

The summary of subject accountability by investigator also will include the number of subjects who enrolled in the study, completed the study, discontinued study drug, and

subjects in the mITT 1, mITT 2, Safety Population 1, and Safety Population 2, respectively.

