6.0 Study Treatment Duration and Compliance

Duration of treatment for atogepant, defined for each subject as last dose date minus first dose date + 1, will be summarized for the Safety Population 1 and Safety Population 2.

Duration of treatment for atogepant will be summarized for each period (open-label atogepant period or open-label atogepant + ubrogepant period) and the entire open-label period using the number of subjects treated, mean, standard deviation, median, minimum and maximum. In addition, the number and percentage of subjects in each treatment duration of ≥ 1 day, ≥ 7 days, ≥ 14 days, ≥ 21 days, ≥ 28 days, ≥ 35 days, ≥ 42 days, ≥ 49 days, ≥ 56 days, ≥ 63 days, ≥ 70 days, ≥ 77 days, ≥ 84 days, ≥ 91 days, ≥ 98 days, ≥ 105 days, ≥ 112 days, ≥ 119 days, ≥ 126 days, ≥ 133 days, ≥ 140 days, ≥ 147 days, ≥ 154 days, ≥ 161 days, ≥ 168 days will be summarized.

Duration of treatment for ubrogepant, defined as the number of doses and days of ubrogepant taken, will be summarized for the Safety Population 2, by the number of subjects treated, mean, standard deviation, median, minimum and maximum.

Treatment compliance of atogepant for a specific period (open-label atogepant period and open-label atogepant + ubrogepant period) is defined as the number of atogepant doses actually taken by a subject during that period divided by the number of atogepant doses that were expected to be taken during the same period multiplied by 100. Percent treatment compliance will be summarized in each period for the Safety Population 1 and Safety Population 2.

Ubrogepant is taken as needed, so no treatment compliance will be provided for ubrogepant.

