10.0 Safety Analyses

10.1 General Considerations

The safety analyses will be performed using the Safety Population 1 or 2. The safety endpoints include AEs, clinical laboratory evaluations, vital sign measurements, ECG parameters, the C-SSRS, and pregnancy test. For each of the clinical laboratory, vital sign, and ECG parameters, the last non-missing safety assessment before the first dose of study drug will be used as the baseline for all analyses of that safety parameter.

Continuous variables will be summarized by the number of subjects, mean, standard deviation (SD), median, Q1, Q3, minimum, and maximum values. Categorical variables will be summarized by number and percentage of subjects.

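### SAP 10.6 classes subjects by total ubrogepant use over the whole concomitant period, so stopping early lowers the class and biases the discontinuation row toward lower rates at higher use

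*SAP*

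**What the plan says.** SAP 10.6 defines four groups (never, low, moderate, high) in two ways. By days of use they are 0, 1-3, 4-9 and 10 or more; by doses they are 0, 1-6, 7-18 and 19 or more. Each count is a total over the concomitant period, for example "Low ubrogepant use: 1-3 days of ubrogepant taken in the atogepant + ubrogepant treatment period". Three outcomes are then tabulated: "TEAE, serious TEAE, and TEAE leading to study drug discontinuation will be summarized by subgroups". SAP 10.1 makes the summary a number and percentage of subjects.

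Protocol 5.5 lists among the reasons for withdrawal "Clinically significant abnormal laboratory results or AEs, which rule out continuation of the study drug".

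Section 10.6 names neither the population nor the onset window, and SAP 10.1 says only that "The safety analyses will be performed using the Safety Population 1 or 2". Two other sections point to Safety Population 2. SAP 5.0 defines it as subjects who "took at least one dose of study drug, either atogepant or ubrogepant, during the open-label atogepant + ubrogepant treatment period". SAP 6.0 summarises ubrogepant exposure, "defined as the number of doses and days of ubrogepant taken, will be summarized for the Safety Population 2".

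Nothing in SAP section 10 restricts use to the time before onset, sets a landmark or uses person-time. The Kaplan-Meier curves in SAP 10.2.3 cover a few named AEs and are not split by use.

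**The concern.** The outcome helps to set the exposure group. A subject who stops early has had less time to accumulate days or doses, so the event is counted in a lower group than the subject's rate of use would imply. Subjects with the same rate of use who complete the period stay in the higher group and dilute its rate.

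The primary objective is the safety of concomitant use, and this is the only planned summary that relates the amount of ubrogepant taken to AEs. The error is in the reassuring direction: the row can fall with use when there is no effect, or hide part or all of a real increase. The interim in SAP 11.0 covers all safety analyses and is meant to support access and reimbursement negotiations, so the table may have readers outside the study team.

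**Working it through.** **1. The plan's own figures.** SAP 2.4 gives 235 enrolled and 15% dropout in the first period: 235 × 0.85 = 199.75, or about 200. The half-width 1.96 × √(p(1−p)/200) is 3.0% at p = 5% and 4.95% at p = 15%, which reproduces the stated 3% to 5% for the whole group. The plan states no figure for the 10.6 table.

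**2. Direction.** Expected use by stop day t is (full-period use) × t/84. A subject on course for 12 use days who stops on day 21 has 12 × 21/84 = 3 days and is classed Low, not High. One on course for 20 doses has 20 × 21/84 = 5 doses, again Low and not High. No assumption about ubrogepant's effect is involved.

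**3. Assumed inputs for size (none is in the documents except 200 subjects and 84 days).**
- AE stops 3% (200 × 0.03 = 6 events); other dropout 5%.
- Expected use gamma-distributed with mean 6 days per 84 and CV 1.0, capped at 24 (equal to the plan's 8 treated headaches per 4 weeks × 3).
- A second dose on 35% of use days.
- Stops spread evenly, early (half by day 21) or late (half after day 59).
- Lag from onset to stop either zero or exponential with mean 7, 14 or 28 days.

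**4. Simulated long-run results, classes by days.** With no effect, even stops and no lag, the 10.6 classes show 6.1/3.6/2.0/1.0% (never/low/moderate/high) against a true 2.9% in every class. About 46% of AE stoppers land in a lower class than they would have reached.

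| Stopping pattern | No effect: low-to-high ratio (true 1) | Stop risk proportional to use rate: table shows (true 0.4/1.2/3.0/6.9%) |
|---|---|---|
| Even, no lag | 3.6 | 2.6/3.0/3.0/2.8% |
| Even, lag 7 days | 2.8 | 1.9/2.8/3.2/3.4% |
| Even, lag 14 days | 2.3 | 1.5/2.5/3.4/4.0% |
| Even, lag 28 days | 1.8 | 1.2/2.1/3.2/4.7% |
| Early, no lag | about 5 | 5.5/3.2/2.1/1.7% |
| Late, no lag | 2.3 | 1.1/2.3/3.4/4.2% |

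A grid of 54 combinations (AE stops 2/3/5%, mean use 4/6/9 days, CV 0.7/1.0/1.3, other dropout 0/10%) gave no-effect ratios of about 2.4 to 6. It varied neither timing nor lag, so it is not a bound.

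**5. Risk only on use days.** A separate model (gamma shape 1.5, mean 7 use days, 0.5% risk per use day, no lag) has true rates of 0/1.0/3.0/7.3%. The 10.6 classes show 0/4.3/3.5/3.0%. Never versus any use still separates; the gradient among users is lost.

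**6. One trial, about 6 events, no lag.** With no effect, never+low exceeds moderate+high in 88% of runs, but the full four-step gradient appears in only about 18%. With risk proportional to use rate, moderate+high exceeds never+low in 50% of runs under the 10.6 classes, against 87% under a Weeks 13-16 landmark by days and 85% by doses.

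**7. Alternatives, base case.** The landmark by days gives 2.0/2.0/2.0/1.9% with no effect and 0.7/1.3/2.2/4.5% when risk rises with use. Cumulative use to date with person-time gives 3.0/3.0/3.0/3.1 per 100 subject-periods of 84 days with no effect, and 1.4/2.6/4.7/8.1 when risk rises with use.

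**The case against.** What ends use is the stop, not the onset, and Protocol 5.5 does not say that one follows the other at once. This stands, and it matters: with a lag of 7 to 28 days the no-effect ratio roughly falls to between 2.8 and 1.8, and a real increase still shows, though weakened. The bias is also smaller if a subject stops only atogepant.

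The row is descriptive and rests on few events. AEs are listed by subject (SAP 3.3, 10.2.4) and a DMC reviews safety. This limits the consequence. It does not correct the percentages, and a sparse table with a built-in direction is easy to misread.

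The landmark has its own weaknesses. It sets events aside, its never group includes subjects who first use ubrogepant after Week 16, and it cannot separate a drug effect from migraine frequency. All of this stands. In particular, risk proportional to a subject's use rate could equally reflect migraine burden.

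Several stronger readings are tempting. A reader might infer that the table will come out flat or reversed. That needs zero lag or early stops, and the documents establish neither. A reader might extend the bias to all three rows. Serious TEAEs are affected only so far as they stop treatment, and any-TEAE rates have no predictable direction because high users also spend longer on treatment. A reader might think the primary safety results are compromised. The period-level tables in SAP 10.2.1 to 10.2.4 do not use these classes. Finally, a reader might conclude that first-period stoppers will be counted as never-users; SAP 5.0 and 6.0 point to Safety Population 2, so this calls only for clarification.

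**Conclusion.** The point holds for one row of one table. Classing by total use builds in a bias toward lower discontinuation rates at higher use, and no other section corrects it. The direction is certain on average; the size is not known. Under the assumptions shown, the no-effect low-to-high ratio runs from about 1.8 (28-day lag) to about 5 (early stops, no lag), where the truth is 1. A real gradient is attenuated, flattened or reversed depending on timing and lag, and a single trial with about 6 events may not display the pattern at all. The change should be made, because it is cheap and the row bears on the safety of concomitant use, but the main safety conclusions do not depend on it.

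**What to change.** Amend SAP 10.6 as follows.

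1. For TEAEs leading to discontinuation, classify by ubrogepant use before onset.
   - If doses are dated, use cumulative use to date with person-time denominators.
   - Otherwise, use a Visit 6 landmark by doses: group by use in Weeks 13-16 and count later events among subjects still on treatment. One third of the SAP's cut-points gives 0, 1-2, 3-6 and 7 or more doses. Show events before the landmark alongside the table so that none is dropped.
2. Footnote any total-use table that is kept: use is truncated by discontinuation, and the table does not show an exposure-response relationship. The footnote should add that neither alternative separates a drug effect from migraine frequency.
3. State Safety Population 2 and onset in the concomitant period.

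The cost is SAP wording and modest programming. Doses per 4-week interval should be obtainable: ubrogepant is dispensed at Visits 5 to 7, Protocol Appendix D schedules "Perform drug reconciliation" at each visit from Visit 3 to Visit 8, and Protocol 5.7 states that "All subject dosing will be recorded". The documents do not show whether each dose is dated, so the person-time version is conditional on that.

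The landmark sets aside about 34% of discontinuation events in the base case, leaving 6 × 0.66 = about 4, and from 11% (late stops) to 59% (early stops) otherwise. With so few events expected, the footnote is the minimum.

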11.0 Interim Analyses

An interim analysis that includes all safety and efficacy analyses is planned when at least 30 subjects have completed Visit 8 to support access/reimbursement negotiations.

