7.6 Interim Analysis

An interim analysis that includes all safety and efficacy analyses is planned when at least 30 subjects have completed Visit 8 to support access/reimbursement negotiations.

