2.4 Sample Size Determination

Approximately 235 subjects will be assigned to receive open-label atogepant 60 mg once daily for the preventive treatment of episodic migraine at Baseline/Visit 2 (Day 1). Based on historical data from previously completed clinical studies, it is assumed that 15% of subjects will discontinue from the study during the atogepant treatment period (Day 1 to Week 12). Therefore, approximately 200 subjects will be assigned to also receive ubrogepant 100 mg for the acute treatment of migraine starting at Visit 5 (Week 12).

This sample size will provide estimation for AEs of interest occurring in either the open-label atogepant treatment period (Day 1 to Week 12) or the open-label atogepant and ubrogepant concomitant use treatment period (Weeks 12 to 24) with a precision (defined as the half width of 95% confidence interval) of approximately $\pm 3\%$ to 5%.

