4.0 Analysis Populations

The modified intent-to-treat 1 (mITT1) population includes all enrolled subjects who received at least 1 dose of study drug, have a baseline assessment, and have at least 1 postbaseline assessment during the open-label atogepant treatment period. The modified intent-to-treat 2 (mITT2) population includes all enrolled subjects who received at least 1 dose of study drug, have a baseline assessment, and have at least 1 postbaseline assessment during the open-label atogepant + ubrogepant treatment period. The mITT1 or mITT2 populations will be used for all efficacy analyses.

The Safety Population 1 consists of all subjects who received at least 1 dose of study drug during the open-label atogepant treatment period. The Safety Population 2 consists of all subjects who received at least 1 dose of study drug during the open-label atogepant + ubrogepant treatment period. The Safety Population 1 or Safety Population 2 will be used for safety analyses.

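### The interim has no data cut-off or analysis set; if all dosed subjects are used, crude TEAE percentages understate 12-week incidence, more so in the concomitant-use period

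*SAP*

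**What the plan says.** SAP 11.0 states: "An interim analysis that includes all safety and efficacy analyses is planned when at least 30 subjects have completed Visit 8". Protocol 7.6 has the same sentence, and both name access and reimbursement negotiations as the purpose. Nothing more is said about it. SAP 2.2 points to Section 10.6 for details, but that section covers safety subgroups.

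On who is counted, SAP 4.0 puts everyone with one or more doses in the concomitant-use period into Safety Population 2. Safety Population 1 has the same form for the atogepant-alone period. Neither sets a minimum follow-up.

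On what is reported, SAP 10.1 states: "Categorical variables will be summarized by number and percentage of subjects". SAP 10.2.1 applies this to TEAEs for each period and for the whole treatment period. No exposure-adjusted rate is planned. Kaplan-Meier curves (SAP 10.2.3) cover nausea, constipation, fatigue/somnolence and decreased appetite only, over the entire open-label period. Atogepant duration is tabulated by period (SAP 6.0) but not used to adjust AE percentages.

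On size, SAP 2.4 plans about 235 subjects, assumes 15% stop in the first 12 weeks, and expects that "approximately 200 subjects will be assigned to also receive ubrogepant 100 mg for the acute treatment of migraine starting at Visit 5".

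**The concern.** The trigger counts subjects who have finished, while the tables count subjects who have started. With staggered entry the two groups differ. A subject one week into the concomitant-use period adds a full unit to the denominator and about one week of risk to the numerator. Period 2 is hit harder because every subject reaches it 12 weeks later.

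Safety of concomitant use is the primary objective, and the only within-study reference for it is the atogepant-alone period. The interim is intended for access and reimbursement negotiations, so its percentages will be read outside the study team. A Period 2 figure that is lower because follow-up is shorter could be taken as evidence that adding ubrogepant brings no extra AEs.

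**Working it through.** **The plan's own figures.** 235 × 0.85 = 199.75, which matches the 200 expected in Period 2. SAP 2.4 sizes the study "with a precision (defined as the half width of 95% confidence interval) of approximately" 3% to 5%. The half-width 1.96 × √(p(1−p)/n) at n = 200 is 3.02% for p = 5% and 4.95% for p = 15%. The stated precision therefore reproduces for AE rates of about 5% to 15%.

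**Inputs for the interim.** From the documents: a minimum of 30 completers, two 12-week periods, 235 subjects and 15% dropout in Period 1. Assumed, because the documents are silent: uniform accrual of 235 over A weeks (8 to 208), 10% dropout in Period 2, a true 12-week AE risk of 10%, and a hazard that is either constant or front-loaded (Weibull shape 0.5). All dosed subjects are in the denominator.

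**Timing.** Entries needed for 30 completers: 30/(0.85 × 0.90) = 39.2. The cut falls at T = 24 + 39.2 × A/235 weeks.

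**Worked case, A = 52, constant hazard.**
- Accrual is 235/52 = 4.52 per week, so T = 24 + 39.2/4.52 = 32.7. Enrolled: 4.52 × 32.7 = 148. Safety Population 2: 4.52 × (32.7 − 12) × 0.85 = 79.
- With AE hazard h = −ln(1−risk)/12 and dropout hazard d = −ln(1−dropout)/12, the crude proportion after u weeks is h/(h+d) × (1 − exp(−(h+d)u)).
- Period 2: full-period value 9.50%; average over entrants spread evenly from 0 to 12 weeks 4.91%. The share lacking 12 weeks is 12/20.7 = 58%. Interim: 0.42 × 9.50 + 0.58 × 4.91 = 6.84%. Ratio 6.84/9.50 = 0.72.
- Period 1: full-period value 9.24%; partial average 4.83%. The share lacking 12 weeks is 12/32.7 = 37%. Interim: 0.633 × 9.24 + 0.367 × 4.83 = 7.62%. Ratio 0.82.

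**Range at the minimum trigger** (ratio of interim to full-period crude percentage, Period 1 / Period 2):

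| A (weeks) | T | Enrolled | Safety Pop. 2 | Lacking 12 weeks | Constant hazard | Front-loaded |
|---|---|---|---|---|---|---|
| 8 | 25.3 | 235 | 200 | 0% / 83% | 1.00 / 0.78 | 1.00 / 0.88 |
| 16 | 26.7 | 235 | 183 | 8% / 82% | 1.00 / 0.61 | 1.00 / 0.74 |
| 26 | 28.3 | 235 | 125 | 37% / 73% | 0.86 / 0.65 | 0.92 / 0.77 |
| 52 | 32.7 | 148 | 79 | 37% / 58% | 0.82 / 0.72 | 0.89 / 0.82 |
| 104 | 41.4 | 93 | 56 | 29% / 41% | 0.86 / 0.80 | 0.91 / 0.87 |
| 208 | 58.7 | 66 | 45 | 20% / 26% | 0.90 / 0.88 | 0.94 / 0.92 |

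Period 2 is lower in every row. Its shortfall runs from 8% (ratio 0.92) to 39% (5.75/9.50 = 0.605).

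**A later cut.** At 100 completers the Period 2 ratio (constant hazard) is 0.79 for A = 26 and 0.86 for A = 52. At 150 it is 0.97 and 0.94.

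**Kaplan-Meier by period** (simulated, constant hazard, Period 2). Total error is √(bias² + SD²) against the true risk. For the crude figure, SD = √(p(1−p)/n).

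| True risk | A | Crude | KM (SD) | Total error, crude | Total error, KM |
|---|---|---|---|---|---|
| 10% | 26 | 6.0% | 9.8% (3.7) | 4.5 | 3.7 |
| 10% | 52 | 6.7% | 9.9% (4.2) | 4.3 | 4.2 |
| 10% | 104 | 7.7% | 10.0% (4.7) | 4.2 | 4.7 |
| 30% | 26 | 18.9% | 29.9% (6.0) | 11.6 | 6.0 |
| 30% | 52 | 20.9% | 29.9% (6.5) | 10.2 | 6.5 |
| 30% | 104 | 23.2% | 30.0% (7.3) | 8.8 | 7.3 |

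About 0.5 point of the crude shortfall at 10% comes from Period 2 dropout (9.5% at full follow-up) and would remain at the final analysis.

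**Entry-date cohort** (only subjects enrolled at least 24 weeks before the cut). This keeps 39 subjects in Period 1 and 39.2 × 0.85 = 33 in Period 2. At a true 10% its Period 2 error is √(0.10 × 0.90/33.3) = 5.2 points. The all-dosed crude figure has 4.1 to 4.2 under accrual of 3 to 8 per week. At 30% the order reverses: 7.9 against 8.6 to 10.7.

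**The case against.** **The interim set is not stated.** The shortfall follows only if the Safety Populations are applied as defined. That is the natural reading of running all safety analyses, but a set of Visit 8 completers is possible. It would avoid this shortfall but could leave out subjects who stopped early. Visit 8 also doubles as the early termination visit, so completing it may include early terminators. The count of 39 entries is then not fixed, and the cut could come sooner. This stands, and it is why the point is conditional.

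**Thirty is a minimum.** The tabulated figures are for the earliest permitted cut; a later one shrinks the effect. This stands.

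**The plan has mitigations.** The Kaplan-Meier curves handle censoring for the named AEs, and the duration tables would show the shorter Period 2 follow-up. Neither corrects the by-period percentages for any TEAE, serious TEAEs or discontinuations.

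**The harm may be small.** No comparison between periods is planned. With accrual of 3 to 8 per week and equal true risks of 10%, the artificial gap between periods is 0.8 to 1.4 points, against a Period 2 half-width of 4.5 to 6.5. At 30% it is 2.2 to 4.2 points against 7 to 10. The gap would be hard to tell from noise. It nevertheless has a known direction, and it flatters the combination.

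**A reader might infer that most enrolled subjects are still partway through a period at the cut.** The documents give no accrual rate. It is true in this model only if enrolling 235 takes less than about 105 weeks: 71% are partway at 26 weeks, 35% at 208. The shortfall does not need a majority.

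**Conclusion.** The point holds in conditional form. The interim cut-off and analysis set are undefined. If all dosed subjects are tabulated, crude interim TEAE percentages understate 12-week incidence, and Period 2 is affected more than Period 1 in every scenario tried. At the minimum trigger the relative Period 2 shortfall is roughly 8% to 39%: 12% to 39% with a constant hazard and 8% to 26% with a front-loaded one. Direction and ordering are stable. The size rests on assumed accrual, Period 2 dropout and hazard shape.

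Three stronger readings are not supported. The documents do not establish that the interim figures will be wrong, because the set is not specified. The final analysis is not affected by staggered entry. Nothing here extends to the responder rates, since descriptive efficacy summaries use observed cases (SAP 9.2) and no shortfall has been shown for them.

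This should be settled before the interim is run, because its output is meant for outside use on the primary objective.

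**What to change.** In SAP 11.0:

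- State the data cut-off rule, whether an early termination Visit 8 counts towards the 30, and that the interim set is all dosed subjects. Correct the pointer in SAP 2.2.
- For any TEAE, serious TEAEs, TEAEs leading to discontinuation and common TEAEs, report Kaplan-Meier 12-week cumulative incidence in each period, censoring ongoing subjects at the cut-off. Exposure-adjusted rates by period are an acceptable alternative. Show these beside the crude counts.
- Label the crude interim percentages as based on incomplete follow-up.
- An entry-date cohort may be added as a sensitivity analysis. It should not replace the all-dosed tables, because with about 33 subjects in Period 2 its total error is larger than that of the crude figure for AE rates around 10%.

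The cost is one paragraph, a few extra interim tables, and wider Period 2 intervals (SD about 4 to 5 points at a 10% risk). The trigger and timing do not change.
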